9.8.2 Analyses of Biomarker Endpoints

The analysis of biomarker will be described and performed by Clinical Biomarker Group.

10. Changes From Protocol-specified Analyses

There are no changes to the protocol-specified analyses.

11. Literature Citations / References

12. Prioritization of Analyses

There is no prioritization of analyses.

13. Data Not Covered by This Plan

The analyses of PK and biomarkers are not covered by this plan.

14. Appendices

Appendix A. Imputation Rules

Imputation Rules for Partial or Missing Dates for Adverse Events and Concomitant Medications

Imputation Rules for Partial or Missing Start Dates

Start Date		Stop Date						missing
		Complete: yyyymmdd		Partial: yyyymm		Partial: yyyy		
		< 1 st dose	≥ 1 st dose	< 1 st dose yyyymm	≥ 1 st dose yyyymm	< 1 st dose yyyy	≥ 1 st dose yyyy	
Partial: yyyymm	= 1 st dose yyyymm	2	1	2	1	n/a	1	1
	≠ 1 st dose yyyymm		2		2	2	2	2
Partial: YYYY	= 1 st dose YYYY	3	1	3	1	n/a	1	1
	≠ 1 st dose YYYY		3		3	3	3	3
Missing		4	1	4	1	4	1	1

1 = Impute the date of first dose
 2 = Impute the first of the month
 3 = Impute January 1 of the year
 4 = Impute January 1 of the stop year

Note: If the start date imputation leads to a start date that is after the stop date, then do not impute the start date.

Imputation rules for partial or missing stop dates:

- Initial imputation
 - a. For partial stop date mmyyyy, impute the last of the month.
 - b. For partial stop date yyyy, impute December 31 of the year.
 - c. For completely missing stop date, do not impute.
- If the stop date imputation leads to a stop date that is after the death date, then impute the stop date as the death date.
- If the stop date imputation leads to a stop date that is before the start date, then set the stop date as missing.

Imputation rules for partial or missing death dates:

- If death year and month are available but day is missing:
 - a. If YYYYMM for the date last known to be alive equals YYYYMM for death date, set death date to the day after the date last known to be alive.

- b. If YYYYMM for the date last known to be alive is less than the YYYYMM for death date, set death date to the first day of the death month.
- c. If YYYYMM for the date last known to be alive is greater than YYYYMM for death date, data error, do not impute and censor subject survival time.
- If month and day are missing and year of death is known:
 - a. If YYYY for the date last known to be alive equals the YYYY for death date, set death date to the day after last known to be alive date.
 - b. If YYYY for the date last known to be alive is less than the YYYY for death date, set death date to the first day of the death year.
 - c. If YYYY for the date last known to be alive is greater than YYYY for death date, data error, do not impute and censor the subject survival time.
- If a death date is totally missing, do not impute and censor the subject survival time.

General Imputation rules for time to event efficacy endpoints

Unless otherwise specified, the partial/missing event dates will be imputed as follows:

- If event year and month are available but the day is missing:
 - a. If mmyyyy for the date last known to be event-free equals mmyyyy for event date, set event date to the day after the date last known to be event-free.
 - b. If mmyyyy for the date last known to be event-free is less than the mmyyyy for event date, set event date to the first day of the event month.
 - c. If mmyyyy for the date last known to be event-free is greater than mmyyyy for event date, data error and do not impute.
- If month and day are missing and year of event is known:
 - a. If yyyy for the date last known to be event-free equals the yyyy for event date, set event censor date to the date last known to be event-free.
 - b. If yyyy for the date last known to be event-free is less than the yyyy for event date, set OS censor date to last day of the prior year.
 - c. If yyyy for the date last known to be event-free is greater than yyyy for event date, data error and do not impute.
- If an event date is totally missing, do not impute.

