- **IMWG-URC for MM**
- **2017 ELN criteria for AML**
- **Revised IWG for MDS**
- **Lugano Classification for NHL**

Dose Limiting Toxicity (DLT)

Unless otherwise specified, investigators determine whether an adverse event qualifies as a DLT per the definition described in the protocol.

DLT Observation Period

The DLT observation period is defined as, at minimum, 28 days after the initial dose of AMG 397. If lead-in dosing period is initiated, the DLT-observation period is defined as the amount of time for subject(s) for each dose cohort to receive at least 1 week of lead-in dose and 3 weeks of target dose.

Duration of Response (DOR)

Duration of response is calculated for subjects who have achieved response (PR or better). It is defined as time from the first observation indicating a response to the subsequent date of disease progression or death, whichever is earlier.

DOR time in months: (date of disease progression or death - date of the first observation of response +1)/30.4

Subjects without disease progression or death until the analysis data cut-off date will be censored at the last adequate disease assessment date.

Fridericia-corrected QT Interval (QTcF)

The Fridericia correction will be calculated from the investigator reported QT (msec) and RR interval (msec): $QTcF = QT / (RR/1000)^{1/3}$

Investigational Product (IP)

IP is used in reference to AMG 397.

Overall Response Rate (ORR)

ORR is the incidence of either PR or better based on investigator assessment. All subjects that do not meet the criteria for response (PR or better) by the analysis cutoff date will be considered as non-responders.

Progression-free survival (PFS)

PFS time is calculated as time from first dose of IP date to disease progression date or death due to any cause, whichever is earlier.

PFS time in months: (date of disease progression or death - first dose of IP date +1)/30.4

Subjects without disease progression or death until the analysis data cut-off date will be censored at the last adequate disease assessment date. If no post-baseline disease assessment, censoring is at the first dose of IP date.

Overall survival (OS)

OS is defined as the time from first dose of IP date until death due to any cause.

OS time in months: (date of death - first dose of IP date +1)/30.4

Patients without event will be censored at their last date known to be alive.

Study Day

Post study day 1: study day = (date –Study Day 1) + 1

Pre study day 1: study day = (date –Study Day 1)

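### SAP Appendix A censors a known death when its date is wholly missing; this is inconsistent with the SAP's own OS definition and pushes Kaplan-Meier OS upward

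*SAP*

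**What the plan says.** Four pieces of SAP text bear on this.

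- **Section 5, Overall survival, event:** "OS is defined as the time from first dose of IP date until death due to any cause".
- **Section 5, Overall survival, censoring:** "Patients without event will be censored at their last date known to be alive".
- **Appendix A, partial or missing death dates:** the list branches on how much of the date is known. With only the year known, and last contact in that same year, the instruction is "set death date to the day after last known to be alive date". With last contact in an earlier year it is "set death date to the first day of the death year". If the partial date precedes the last date known alive, it is "data error, do not impute and censor the subject survival time". If no part of the date is known: "If a death date is totally missing, do not impute and censor the subject survival time".
- **Appendix A, general rules for time-to-event endpoints:** these open with "Unless otherwise specified, the partial/missing event dates will be imputed as follows". For a year-only date with the last event-free date in an earlier year, they say "set OS censor date to last day of the prior year". For a wholly missing event date they say not to impute, and do not state whether the subject counts as an event or as censored.

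Section 9.5 analyses OS, PFS and DOR by Kaplan-Meier on the Full Analysis Set. Section 2.2 rules out formal hypothesis testing.

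**The concern.** The last death-date branch takes a subject whose death is established and analyses that subject as if still alive at last contact. Kaplan-Meier estimation assumes that censored subjects have the same future risk as those who stay under observation. Here the subject is censored because of the death, so the assumption fails in a known direction: an event disappears and the curve sits too high from that point on.

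The groups are small. SAP section 3.2 plans up to 20 subjects per expansion group and up to 6 in Part 2B, and section 9.1 summarizes efficacy by dose level within indication. Section 9.5 also allows time-to-event summaries to be dropped below 10 events, so a discarded death could decide whether an OS summary appears at all.

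**Working it through.** The plan states no OS rate or event count, so there is no figure of its own to reproduce. The check has two parts: the text side by side, then the size of the bias under stated assumptions.

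**1. The text**

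| Subject | Section 5 | Appendix A, death dates |
|---|---|---|
| No death recorded | Censored at last date known alive | Not addressed |
| Death recorded, only year known, same year as last contact | Event | Event, day after last known alive |
| Death recorded, only year known, last contact in an earlier year | Event | Event, first day of that year |
| Death recorded, date wholly missing | Event | Censored |

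The mismatch is in the last row. The rule sits among the rules for death dates, and a living subject has no death date to be missing, so it can only concern recorded deaths. It does not name the censoring date; section 5 supplies the last date known alive.

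**2. Size for one death**

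Let r be the number at risk at the true death time, and suppose no other death or censoring falls between last contact and that death. Counted, the death contributes a factor (r − 1)/r. Censored, it contributes 1. Both ways leave r − 1 at risk afterwards, so every later estimate is multiplied by r/(r − 1).

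Assumed example: 20 subjects, one death at each of months 1 to 10, the other 10 censored at month 12. The month-5 death is undated, with last contact at month 4.5.

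- *All deaths counted:* 6 months, 14/20 = 70.0%; 12 months, 10/20 = 50.0%.
- *SAP rule:* four deaths by month 4 give 16/20 = 0.80. After the censoring at 4.5, 15 are at risk at month 6. At 6 months, 0.80 × 14/15 = 74.7%. At 12 months, 0.80 × 10/15 = 53.3%.
- *Formula check:* r = 16, and 70.0% × 16/15 = 74.7%; 50.0% × 16/15 = 53.3%.
- *Counted the day after last known alive (4.5 + 1/30.4 months):* the order of deaths is unchanged, so 70.0% and 50.0% return.
- *Two undated deaths (months 3 and 5, last contact 2.5 and 4.5):* 6 months, 0.90 × 16/17 × 14/15 = 79.1%; 12 months, 0.90 × 16/17 × 10/15 = 56.5%.

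**3. Average size by share of undated deaths**

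Simulation, all inputs assumed: n = 20, exponential OS with median 6 months, 12 months of follow-up, 3,000 runs per setting. Last contact falls uniformly within 1 month, or within 3 months, before death; ranges span these two cases. The 12-month value is read just before month 12.

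| Undated share | 6-month OS: all dated / SAP rule / day after | 12-month OS: all dated / SAP rule / day after |
|---|---|---|
| 5% | 49.8% / 51.4–51.5% / 49.5–49.7% | 24.8–24.9% / 26.4–26.5% / 24.8–24.9% |
| 10% | 50.3% / 53.4–53.7% / 49.5–50.0% | 25.0–25.1% / 28.2–28.6% / 25.0–25.1% |
| 20% | 50.1–50.2% / 56.5–57.4% / 48.7–49.6% | 25.1% / 32.1–32.8% / 25.1% |

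The SAP rule biases upward in every setting. The day-after convention is slightly low at 6 months and unbiased at 12 in this set-up.

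**The case against.** **The case may never arise.** In the supplied protocol (section 7.4.5), long-term follow-up is every 3 months for up to a year from first dose, by telephone or chart review, in expansion subjects only. A death learned of at such a contact usually lies between two known dates, so at least the year would often be known and a partial-date branch would apply. This stands as an argument for low frequency. It does not exclude intervals that cross a year-end, missed contacts, or the public-record searches for survival status in protocol section 12.4. The SAP implements protocol amendment 4, which is not supplied, so the follow-up procedure in force cannot be checked.

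**The consequence is small.** OS is secondary and untested, and subject-level data are provided if a summary is dropped. This also stands, and it limits the weight of the point.

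**Censoring without a usable date is at least consistent.** The data-error branch censors too. But that branch handles a date that contradicts other data. The day-after convention needs no part of the death date, only the last date known alive, so it is available for undated deaths.

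**Stronger readings that do not hold.** A reader might infer that the rule contradicts the partial-date rules. It does not: known month, known year and nothing known are separate branches, and no record gets two answers from that list. The treatment is uneven, not contradictory. A reader might also infer that each case removes a PFS event. The quoted rule concerns survival time only, the general rules leave event status unstated, and a subject who progressed first already has a PFS event.

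**Conclusion.** The point holds as an inconsistency between Appendix A and section 5, with a known direction of bias. A confirmed death is censored where section 5 reserves censoring for patients without an event, and Kaplan-Meier OS is pushed upward.

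The size depends on assumptions. One undated death in the 20-subject example adds 4.7 points at 6 months and 3.3 at 12. A reader might take 1/n (5 points at n = 20, 10 at n = 10) as the maximum for one death; it is not. That step applies immediately after the death when nobody was censored earlier. With 20 subjects, no earlier deaths and 10 already censored, one death moves the curve by 1/10, or 10 points. Nor do the documents support saying that reported OS will be materially wrong: the share of undated deaths is unknown, and with none the effect is zero.

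A related defect should be corrected at the same time. For a year-only date with last contact in an earlier year, the death-date rules set a death date, while the general rules set a censoring date and name OS in doing so. The opening proviso of the general rules probably lets the death-date rules govern OS, but the OS wording should not remain.

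This is a minor correction, worth making before analysis because it costs so little.

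**What to change.** In SAP Appendix A, replace the branch for a wholly missing death date with wording such as: a confirmed death whose date is totally missing is counted as an OS event on the day after the last date known alive, is flagged in the listing, and the number of such deaths is reported.

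Then make two consequential edits in the general time-to-event rules:

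- State that the same imputation applies to PFS only when death is the first PFS event.
- Align the year-only branch that sets an OS censoring date with the death-date rules, which set a death date.

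If the team prefers to keep censoring as the main rule, the day-after analysis should be given as a sensitivity analysis, with the number of undated deaths stated.

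The cost is a few lines of SAP text and a small programming change, with no extra data collection. If such a case occurs, OS becomes slightly less favourable, and the imputed date slightly shortens that subject's survival time.

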#### **7.4.5 Long-term Follow-up (Dose expansion subjects only)**

Long-term follow up (LTFU) will be conducted every 3 months from the last visit for up to 1 year from the first dose of AMG 397 for all subjects who have not withdrawn consent by telephone or chart review to assess for survival, disease progression and/or the commencement of subsequent cancer therapy only.

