8.3 Handling of Missing and Incomplete Data

The following imputation of missing values will be done:

Incomplete adverse event, concomitant medication dates and dates used for the derivation of time to efficacy endpoints will be imputed as per [Appendix A](#).

Non-pharmacokinetic measurements that are above or below the quantification limits will be considered equal to the upper or lower limit of quantification for all analyses unless explicitly noted otherwise.

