9.5 Efficacy Analyses

Table 2. Efficacy Endpoints

Endpoint	Statistical Analysis Methods
Overall response rate	The proportion of subjects with response to treatment with corresponding 2-sided exact 95% CI will be calculated using the Clopper-Pearson method (Clopper and Pearson, 1934) for the Full Analysis Set. Refer Appendix B for code fragment.
DOR, PFS, and OS	Kaplan-Meier estimates and Kaplan-Meier curve will be provided for the Full Analysis Set.
TTR	Descriptive statistics will be provided for subjects with response.
MRD[-] status at CR (Parts 3B and 3C only)	Proportion of MRD[-] at CR will be provided for subjects with CR.

For time to event endpoints (including DOR, TTR, OS, and PFS), summary table or figure may not be generated if the number of events is less than 10. The individual subject-level data will be provided.

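### A progression recorded with only its year is censored rather than counted, which drops a known event from PFS and DOR

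*SAP*

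**What the plan says.** SAP Section 8.3 states that incomplete "dates used for the derivation of time to efficacy endpoints will be imputed as per" Appendix A. The general rules for time-to-event efficacy endpoints in that appendix apply unless another rule is specified, and they distinguish two kinds of partial date.

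- **Month and year known.** An event date is set. In the same month as the last event-free date it is the next day; in a later month the instruction is "set event date to the first day of the event month".
- **Year only.** A censor date is set. In the same year as the last event-free date (branch a): "set event censor date to the date last known to be event-free". In a later year (branch b): "set OS censor date to last day of the prior year".

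The death-date rules in the same appendix treat a year-only death differently. In the same year, death is placed on the day after the subject was last known alive; in a later year the instruction is "set death date to the first day of the death year". Both are events.

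SAP Section 5 gives the same censoring sentence for PFS and for DOR: "Subjects without disease progression or death until the analysis data cut-off date will be censored at the last adequate disease assessment date".

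**The concern.** Losing the month should change the date that is assigned, not whether the event happened. Under the year-only branches, a subject whose progression is on record is analysed as if progression had not been seen. Censoring that subject biases the Kaplan-Meier curves for PFS and DOR upward.

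Branch (b) has a second problem: it names OS within a rule for every time-to-event efficacy endpoint. Read literally, it gives PFS and DOR no date at all. Read as meant for them, it censors. For OS itself it collides with the more specific death-date rule. A programmer would have to choose, possibly with the data in view.

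Imprecise progression dates are plausible in long-term follow-up, which Protocol Section 7.4.5 conducts "by telephone or chart review to assess for survival, disease progression and/or the commencement of subsequent cancer therapy only". An event count also matters for reporting: under SAP Section 9.5 a "summary table or figure may not be generated if the number of events is less than 10".

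**Working it through.** The documents give no figure for this rule, so there is none to reproduce. The check compares the rules, works two dates through the SAP's formula, and illustrates the effect on Kaplan-Meier estimates.

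**1. Status given to a recorded event**

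| Information available | Rule | Status |
|---|---|---|
| Progression, month and year | Appendix A, general | Event |
| Progression, year only, same year | Appendix A, general (a) | Censored |
| Progression, year only, later year | Appendix A, general (b) | Censored, or undefined if OS is read literally |
| Death, year only, same or later year | Appendix A, death dates | Event |
| Progression before cut-off | Section 5 | Not among those to be censored |

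The SAP has no other rule for partial progression dates, so the allowance for rules specified elsewhere covers deaths but not progressions.

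**2. Time credited** (Section 5: days from first dose plus 1, divided by 30.4; dates are invented examples)

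- Branch (a): first dose 1 Feb 2021, last event-free 10 May 2021, progression in 2021. The SAP gives 99/30.4 = 3.26 months, censored. The death-type rule gives 100/30.4 = 3.29 months, event.
- Branch (b), read as applying to PFS: first dose 2 Aug 2021, last event-free 20 Nov 2021, progression in 2022. The SAP gives 152/30.4 = 5.00 months, censored on 31 December. The death-type rule gives 153/30.4 = 5.03 months, event on 1 January. Censoring at the last assessment, as in Section 5, would give 111/30.4 = 3.65 months.

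The year-only rules and the death-type rule differ by one day. What changes is the event status. Branch (b) can also censor later than the last disease assessment, here by 152 − 111 = 41 days.

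**3. Effect on a group of 20**

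The size is that of an expansion group in SAP Section 3.2. Assume 10 PFS events at distinct times and the other 10 subjects censored after the last event. Then S = 10/20 = 50.0%. If event j is censored in its own place in the ordering, with no other event moved past it, the factor (20 − j)/(21 − j) drops out:

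- one lost, j = 1: 0.5/(19/20) = 52.6%
- one lost, j = 10: 0.5/(10/11) = 55.0%
- two lost, j = 1 and 2: 0.5/(18/20) = 55.6%
- two lost, j = 9 and 10: 0.5/(10/12) = 60.0%

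With one lost, the count falls from 10 to 9.

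**4. A second scenario**

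Assume 20 subjects, exponential PFS with a median of 4 months represented by evenly spaced quantiles, and 12 months of follow-up. The 6th, then also the 10th, then also the 7th ordered event is recoded as censored.

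| Events lost | Events counted | 6-month PFS | Median (months) |
|---|---|---|---|
| 0 | 18 | 35.0% | 3.7 |
| 1 | 17 | 37.5% | 4.3 |
| 2 | 16 | 41.2% | 4.9 |
| 3 | 15 | 44.4% | 5.7 |

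The direction is the same as in step 3.

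**The case against.** The strongest defence is that the SAP grades dates by quality: a date good to the month makes an event, and a weaker one is censored. Section 5 does not address progressions that cannot be dated, so Appendix A may be read as supplementing it. The death rules also censor some recorded deaths. This does not hold up. The death rules censor only when the date is wholly missing or contradicts the last-alive date; a year-only death is an event. The same imprecision cannot justify the opposite status for a progression.

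Several points of scale do stand.

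- Scheduled disease assessments carry visit dates, so year-only progressions should be rare.
- The telephone and chart-review route applies to expansion subjects only. It comes from protocol amendment 1, whereas the SAP follows amendment 4, which is not available here. Protocol Section 3.5.1 describes the same follow-up without mentioning progression.
- The 10-event threshold is permissive, Section 9.5 provides subject-level data in any case, and the step 3 illustration starts exactly at 10 events.
- The argument is confined to PFS and DOR. Time to response is summarised only in responders.
- PFS and DOR are secondary, no hypothesis is tested, and the dose-level rules do not use them.

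It is also fair to say that assigning the day after the last event-free date tends to shorten PFS and DOR. But that is the convention the SAP already uses for same-month events and same-year deaths, so the fix brings in no new policy. The instruction not to impute a wholly missing event date also leaves a known progression without a stated status; that gap is separate and remains.

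**Conclusion.** The concern holds. As written, the year-only branches remove a recorded progression from PFS and DOR, and branch (b) is additionally mislabelled. The bias is upward. In the 20-subject illustration with 10 events it is 2.6 to 5.0 percentage points for one lost event and 5.6 to 10.0 points for two. These sizes rest on the assumed event pattern and on at least one year-only date occurring; the documents give no frequency, and it is probably low. A later death would not necessarily restore the event, because the SAP does not say whether follow-up continues past the censor date. The wording should be corrected, but the consequence is limited because the endpoints are secondary and descriptive.

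**What to change.** In the year-only part of the general rules in SAP Appendix A:

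- **Branch (a), same year:** assign an event on the day following the last event-free date.
- **Branch (b), later year:** assign an event on 1 January of the event year.
- Delete both references to a censor date, including the one naming OS.
- Add one sentence: partial death dates follow the death-date rules, both for OS and where death is the PFS or DOR event.

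Optionally, add a sensitivity analysis for branch (b) that places the event on the day after the last event-free assessment, because 1 January still credits the gap since that assessment.

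The cost is two lines of SAP text and one sentence. No new data are needed.
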